4.4.3 Management of Cabozantinib Related Adverse Events

The most frequent AEs experienced by $\geq 20\%$ of subjects treated with cabozantinib in descending order of frequency were diarrhea, fatigue, decreased appetite, nausea, PPES, weight decreased, vomiting, hypertension, constipation, asthenia, dysphonia, and AST increased. For a full description of the safety profile of cabozantinib, refer to the current Cabozantinib Investigator's Brochure.

Other medically important but less frequent AEs including arterial thrombotic AEs (e.g., transient ischemic attack [TIA], and myocardial

infarction [MI]) and venous thrombotic AEs (e.g., deep vein thrombosis [DVT] and pulmonary embolism), severe hemorrhagic events, proteinuria, wound healing complications, gastrointestinal (GI) perforation, abscesses including intra-abdominal and pelvic abscess, GI and non-GI fistula formation, osteonecrosis, and reversible posterior leukoencephalopathy syndrome (RPLS).

Adverse events associated with laboratory abnormalities experienced by \geq 5% of subjects treated with cabozantinib in descending order of frequency were AST increased, ALT increased, anemia, hypothyroidism, hypokalemia, hypomagnesemia, thrombocytopenia, hypocalcemia, proteinuria, hypophosphatemia, ALP increased, lactate dehydrogenase (LDH) increased, neutropenia, lipase increased, hyponatremia, platelet count decreased, GGT increased, hypoalbuminemia, leukopenia, and blood TSH increased.

Adverse events may occur within the first few weeks in the course of treatment with cabozantinib, as cabozantinib is expected to reach steady state exposure at approximately 2 weeks following first dose. Events that generally have an early onset include hypocalcemia, hypokalemia, thrombocytopenia, hypertension, PPES, abdominal pain, mucosal inflammation, constipation, diarrhea, and vomiting. Adverse events should be managed with supportive care at the earliest signs of toxicity. Dose reductions and treatment interruptions should be considered. Dose reductions are recommended for events that, if persistent, could become serious or intolerable.

Cabozantinib should be discontinued for the following AEs: visceral perforation or fistula formation, severe hemorrhage, serious arterial thromboembolic events, nephrotic syndrome, hypertensive emergency, persistent uncontrolled hypertension despite optimal medical management, and RPLS.

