4.4.4 Management of Temozolomide Related Adverse Events

The most common adverse reactions ($\geq 10\%$ incidence) are: alopecia, fatigue, nausea, vomiting, headache, constipation, anorexia, convulsions, rash, hemiparesis, diarrhea, asthenia, fever, dizziness, coordination abnormal, viral infection, amnesia, and insomnia.

The most common Grade 3 to 4 hematologic laboratory abnormalities ($\geq 10\%$ incidence) that have developed during treatment with temozolomide are: lymphopenia, thrombocytopenia, neutropenia, and leukopenia.

Allergic reactions have also been reported.

Please refer to [Appendix A](#) for dose modification algorithms for potential combination treatment related adverse events.

Table 0-8: Temozolomide Dosing Interruption or Discontinuation during Treatment Period

Toxicity	Temozolomide Interruption	Temozolomide Discontinuation	Reduce Temozolomide by 1 Dose Level
Absolute Neutrophil Count (ANC)	≥ 0.5 and $< 1.5 \times 10^9/L$	$< 0.5 \times 10^9/L$	≥ 0.5 and $< 1.0 \times 10^9/L$
Platelet Count	≥ 10 and $< 100 \times 10^9/L$	$< 10 \times 10^9/L$	≥ 10 and $< 50 \times 10^9/L$
NCI-CTCAE non-hematological toxicity (except for alopecia, nausea and vomiting)	Grade 2	Grade 3 or 4	Grade 3

Treatment with temozolomide may be continued when all of the following conditions are met:

- $ANC \geq 1.5 \times 10^9/L$
- Platelet count $\geq 100 \times 10^9/L$
- NCI-CTCAE non-hematological toxicity \leq Grade 1 (except for alopecia, nausea and vomiting)

Table 0-9: Temozolomide Dose Levels

Dose 0 (Assigned Starting Dose)	Dose Level 1	Dose Level 0	Dose Level -1
150 mg/m ² /day	200 mg/m ² /day	150 mg/m ² /day	100 mg/m ² /day

Please see [Appendix B](#) for Daily Dose Calculations by Body Surface Area (BSA).

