Grade 2	
 • Cabozantinib treatment may be continued if PPES is tolerated. • Cabozantinib should be dose reduced or interrupted if PPES is intolerable. • Continue urea 20% cream twice daily AND high potency steroid cream (e.g., clobetasol 0.05%) once daily and add analgesics (e.g., NSAIDs/gamma-aminobutyric acid agonists) for pain control if needed. 
Reassess at least weekly; if PPES worsens or affects self-care, proceed to the intervention guidelines for Grade 3.
 
 • Continue temozolomide at the investigator's discretion
Grade 3	
 • Interrupt cabozantinib treatment until severity decreases to Grade 1 or 0. • Continue treatment of skin reaction with high potency steroid cream (e.g., clobetasol 0.05%) twice daily AND analgesics. • Resume study drug at a reduced dose if PPES recovers to Grade ≤ 1. • Discontinue subject from study treatment if PPES does not improve within 6 weeks • Interrupt/continue temozolomide at the investigator's discretion
Proteinuria (UPCR)	
≤ 1 mg/mg (≤ 113.1 mg/mmol)	
 • No change in cabozantinib or temozolomide treatment
> 1 and < 3.5 mg/mg (> 113.1 and < 395.9 mg/mmol)	
 • Refer to Table 0-6 for the management of cabozantinib treatment. No change in temozolomide treatment
≥ 3.5 mg/mg (≥ 395.9 mg/mmol)	
 • Refer to Table 0-6 for the management of cabozantinib treatment. No change in temozolomide treatment.
Nephrotic syndrome	
 • Discontinue cabozantinib
Hepatocellular Toxicity	
Grade 2 AST or ALT or Total Bili lasting longer than a week	
 • Interrupt cabozantinib and temozolomide until Grade 1. • Refer to the Section 4.4.3.13 for the management of DILI
Other Treatment Related Adverse Events (such as fatigue, nausea, vomiting, anorexia, weight loss, etc)	

Grade 1 or Grade 2 (tolerable)	
 • Add supportive care as indicated. • Continue cabozantinib and temozolomide treatment at the current dose; monitor as clinically indicated

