Intolerable Grade 2 or Grade 3	
 • Interrupt cabozantinib and temozolomide treatment until it is a Grade 1 or tolerable grade 2. Restart both cabozantinib and temozolomide at the current dose or dose reduced by one level.^b For Grade 3 AEs related to Temozolomide dose reduce by one level. • *Note: It is recommended that dose holds be as brief as possible
Grade 4-related to temozolomide Grade 4-related to cabozantinib (except clinically non-relevant laboratory abnormalities)	
 • Discontinue temozolomide. • Subjects should have cabozantinib interrupted immediately. • Discontinue cabozantinib unless the following criteria are met: Subject is deriving clear clinical benefit as determined by the investigator Toxicity can be managed with a dose reduction following recovery to Grade 1 (or baseline) and optimal medical care
Study treatment dose adjustment is only needed if the toxicity was deemed related to cabozantinib treatment or had an unclear relationship to cabozantinib treatment. ^b except nausea, vomiting, and alopecia- no dose interruption required for temozolomide	

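### Table 0-8 and Section 4.4.4 hold temozolomide at Grade 2 where Appendix A continues it, Table 0-8 lists Grade 3 under both stop and reduce, and no text says which source governs

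*Combined protocol and SAP*

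**What the plan says.** Section 4.4.4 opens its continuation rule with "Treatment with temozolomide may be continued when all of the following conditions are met". The non-hematological condition is Grade 1 or lower, and alopecia, nausea and vomiting are exempt. Table 0-8 has a matching row with three entries for temozolomide: interrupt at Grade 2, discontinue at Grade 3 or 4, and reduce by one level at Grade 3. Neither text separates tolerable from intolerable Grade 2.

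Appendix A has a general row for other treatment-related events, naming fatigue, anorexia and weight loss among its examples. For Grade 1 or tolerable Grade 2 it says "Continue cabozantinib and temozolomide treatment at the current dose; monitor as clinically indicated". For intolerable Grade 2 or Grade 3 it says "Interrupt cabozantinib and temozolomide treatment until it is a Grade 1 or tolerable grade 2", and then "For Grade 3 AEs related to Temozolomide dose reduce by one level". Grade 4 related to temozolomide means discontinuation. Appendix A also gives temozolomide instructions in its own rows for diarrhea, hypertension, hand-foot syndrome, proteinuria and hepatic toxicity.

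Sections 4.4 and 4.4.4 both point the reader to Appendix A. Section 4.4 presents it as something to take into account. Neither says what to do when it differs from Table 0-8.

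**The concern.** A dose-modification rule should lead two investigators who see the same event to the same action. Here, an investigator using Table 0-8 withholds temozolomide for tolerable Grade 2 fatigue, and one using Appendix A gives it at full dose. Both comply. At Grade 3 the problem sits inside one table row, because a drug cannot be both permanently stopped and restarted one level lower.

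What is at stake is consistent temozolomide exposure and consistent safety handling across the participating sites.

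**Working it through.** No formula applies. The check is a grade-by-grade comparison, for non-hematological toxicity other than alopecia, nausea and vomiting.

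| Situation | Table 0-8 and 4.4.4 | Appendix A | Agree? |
|---|---|---|---|
| Tolerable Grade 2, other events (e.g. fatigue, anorexia) | Hold | Give, dose unchanged | No |
| Restart after a hold, other events | Grade 1 or lower | Grade 1 or tolerable Grade 2 | No |
| Grade 2 diarrhea under 48 h | Hold | Give, dose unchanged | No |
| Grade 2 hand-foot syndrome | Hold | Investigator decides | No |
| Grade 3 hand-foot syndrome | Stop and reduce both listed | Investigator decides | No |
| Grade 3 diarrhea | Stop and reduce both listed | Interrupt, reduce one level | No |
| Grade 3 temozolomide-related other event | Stop and reduce both listed | Interrupt, reduce one level | No |
| Grade 4 diarrhea or temozolomide-related other event | Discontinue | Discontinue | Yes |
| Hypertension | By CTCAE grade | Unchanged in the lower blood-pressure band, investigator decides in the upper | Depends on grade mapping |
| Proteinuria | By CTCAE grade | Unchanged in every UPCR band | Depends on grade mapping |
| Grade 2 hepatic toxicity | Hold | Hold once it lasts over a week, until Grade 1 | Differs in the first week |

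The documents do not print CTCAE grades for the blood-pressure and UPCR bands. How far those two rows conflict with Table 0-8 is therefore an assumption, but they do carry temozolomide instructions of their own.

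**Internal logic of Table 0-8.** For neutrophils, discontinuation is below 0.5 and reduction is 0.5 to below 1.0 (x 10^9/L). For platelets, discontinuation is below 10 and reduction is 10 to below 50. In both rows the reduction range lies inside the interruption range (0.5 to below 1.5, and 10 to below 100) and never meets the discontinuation range. In the non-hematological row, reduction (Grade 3) lies inside discontinuation (Grade 3 or 4) and outside interruption (Grade 2). That row breaks the pattern of the other two.

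**Search for a ruling text.** Sections 4.4 and 4.4.4 give pointers only. Section 4.8 sends the reader back to Section 4.4 and sets no ranking. The Section 4.4 discretion to act on lower-grade toxicity is tied to Table 0-2, the cabozantinib table. It allows more caution, not continuation against the 4.4.4 conditions.

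**The case against.** The strongest defense is scope. Table 0-8 sits under temozolomide-related events and Appendix A covers the combination. A closing footnote in Appendix A says adjustment is needed only when toxicity is related, or of unclear relationship, to cabozantinib. On that reading the two sources deal with different events. It falls short for two reasons. Appendix A itself directs temozolomide-related Grade 3 and Grade 4 events, so it does not stay within that scope. And attribution will often fail to separate the drugs: the common temozolomide reactions in 4.4.4 ("alopecia, fatigue, nausea, vomiting, headache, constipation, anorexia, convulsions, rash, hemiparesis, diarrhea, asthenia, fever, dizziness, coordination abnormal, viral infection, amnesia, and insomnia") and the common cabozantinib events in 4.4.3 ("diarrhea, fatigue, decreased appetite, nausea, PPES, weight decreased, vomiting, hypertension, constipation, asthenia, dysphonia, and AST increased") share fatigue, diarrhea, constipation and asthenia, none of them exempt.

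A second defense is that the Grade 3 intent can be recovered: the hematologic rows and Appendix A both point to reduction at Grade 3, with discontinuation kept for worse events. That is fair, and the double entry is probably a drafting slip. A site reading Table 0-8 alone still finds two actions.

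Third, whether Grade 2 is tolerable is a clinical judgment, so some variation between sites would survive any rewording. That also stands. The rewording removes the conflict between rules, not the judgment.

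A reader might also infer more than the documents support:

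- *A lost course.* Footnote j in Section 5.0 says missed doses are skipped, which suggests that a hold over Days 1-5 costs one of the three courses before the 12-week assessment. But that sentence follows text on holidays and visit windows, and nothing extends it to toxicity holds.
- *A tripped lead-in hold.* Section 10.3 counts subjects who must stop therapy in Cycle 1, so the choice of column at Grade 3 might seem to decide the hold. The rule does not say that stopping temozolomide alone counts, and Cycle 1 temozolomide ends on Day 5. The review of Grade 3 and 4 toxicities after the first 14 subjects takes place either way.
- *A measure of size.* Section 4.4.4 lists 18 common reactions and Table 0-8 exempts three, leaving 18 - 3 = 15. That counts terms in a list, with no grades attached, and says nothing about how many subjects would be dosed differently.

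**Conclusion.** The inconsistency is real and rests on the printed text alone. Tolerable Grade 2 toxicity gets opposite temozolomide instructions, the restart thresholds differ for other events, and Grade 3 has two incompatible actions in one row. No text settles which source prevails.

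Its size in subjects is unknown, because the documents give no rates of Grade 2 or Grade 3 events for the combination. The operating characteristics of the Cohort 1 design are not affected: alpha, power and the 13-of-42 rule do not depend on this. It is a low-cost wording repair that bears on dosing and safety conduct, not a flaw in the statistical design.

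**What to change.** 1. In the Table 0-8 non-hematological row, limit discontinuation to Grade 4 and make Grade 3 interrupt and reduce by one level. Keep discontinuation for Grade 3 hepatic toxicity unless the sponsor writes another rule, because Appendix A has no temozolomide row for it and Section 8.2.2 warns of fatal hepatotoxicity.
2. Add one sentence to 4.4.4: where Appendix A has a row for the event (including diarrhea, hypertension, hand-foot syndrome, proteinuria, hepatic and other), that row governs holding, restarting and reducing temozolomide.
3. Change the Table 0-8 interruption cell to intolerable Grade 2 or Grade 3. Change the 4.4.4 condition to Grade 1 or lower, tolerable Grade 2, or as the Appendix A row for the event states.

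All three are needed. The governing sentence settles hand-foot syndrome, where Appendix A leaves temozolomide to the investigator at Grades 2 and 3.

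The cost is an amendment to wording, with no new data or procedures. The downside is that some subjects stay on temozolomide with tolerable Grade 2 toxicity that Table 0-8 would have held, as Appendix A already permits. This fits the rest of the plan: Table 0-2 continues cabozantinib at tolerable Grade 2, and Section 4.8 uses recovery to tolerable Grade 2 or lower as its threshold. If the sponsor prefers the stricter Grade 2 rule, Appendix A should be tightened instead, so that only one rule stands.

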4.5 Concomitant Medications/Treatments

4.5.1 Allowed Therapy

- Antiemetics and antidiarrheal medications are allowed prophylactically according to standard clinical practice if clinically indicated.

- Granulocyte colony-stimulating factors (G-CSF or GM-CSF) are allowed if used per clinical guidelines (e.g., ASCO or ESMO guidelines).
- Bisphosphonates or RANK-L inhibitors can be used to control bone loss or hypocalcemia if the benefit outweighs the risk per the Investigator's discretion.

Note: osteonecrosis of the jaw has been reported in subjects using bisphosphonates (Section 4.4.3.10). Oral examinations are recommended at screening to determine eligibility and periodically during the study. In addition, subjects should be advised regarding oral hygiene practice and to quickly report symptoms to the Investigator. Frequent monitoring for potentially overlapping toxicities with study treatment is recommended. Withhold cabozantinib for at least 3 weeks prior to scheduled dental surgery or invasive dental procedures, if possible. **Withhold cabozantinib for development of ONJ until complete resolution.**

- Transfusions and hormone replacement should be utilized as indicated by standard clinical practice.
- Individualized anticoagulation therapy with heparin or direct factor Xa inhibitors rivaroxaban, edoxaban, or apixaban is allowed if it can be provided safely and effectively under the following circumstances:
 - At the time of first dose of study treatment:
 - Low dose low molecular weight heparins (LMWH) for prophylactic use are allowed if clinically indicated and the benefit outweighs the risk per the Investigator's discretion.
 - Therapeutic doses of LMWH or the direct factor Xa inhibitors rivaroxaban, edoxaban, or apixaban are allowed if the subject has no evidence of brain metastasis, has been on a stable dose of the

anticoagulant for at least 1 week, and has had no clinically significant hemorrhagic complications from the anticoagulation regimen or the tumor. See [Section 4.5.2](#) for prohibited anticoagulants.

○ After first dose of study treatment:

- Low dose low molecular weight heparins (LMWH) for prophylactic use are allowed if clinically indicated and the benefit outweighs the risk per the Investigator's discretion.
 - Therapeutic doses of LMWH or the direct factor Xa oral inhibitors rivaroxaban, edoxaban, or apixaban are allowed if clinically indicated (e.g., for the treatment of DVT), and the benefit outweighs the risk per the Investigator's discretion. See [Section 4.4.3.5](#) for management of thromboembolic complications while on study. See [Section 4.5.2](#) for prohibited anticoagulants.
- Accepted clinical guidelines regarding appropriate management while receiving any kind of anticoagulation therapy must be followed. This includes, but is not limited to, subject education regarding the potential adverse drug reactions, monitoring laboratory parameters, dose adjustments (e.g., due to kidney dysfunction). Caution is warranted in settings associated with an increased risk for bleeding such as gastrointestinal cancers, urothelial cancers, gastrointestinal mucosal abnormality (e.g., mucositis), renal or hepatic impairment, thrombocytopenia, arterial hypertension, or prior history of gastrointestinal bleed. For direct factor Xa inhibitors, the potential for drug-drug interaction with other concomitant medications, as well as gastrointestinal absorption, should be considered. Aspirin and other nonsteroidal anti-inflammatory drugs (NSAIDs) should not be used concomitantly with heparin or factor Xa inhibitors due to the

increased risk for bleeding complications. The risks and benefits of the use of anticoagulants should be reassessed on a regular basis. For more information regarding the use of anticoagulants, refer to the prescribing information of the anticoagulant and accepted clinical practice guidelines.

Potential drug interactions with cabozantinib are summarized in [Section 4.5.3](#).

4.5.2 Prohibited or Restricted Therapy

The following therapies are prohibited until study treatment has been permanently discontinued:

- Any investigational agent or investigational medical device.
- Oral anticoagulation with coumarin agents (e.g., warfarin), direct thrombin inhibitors (e.g., dabigatran), direct factor Xa inhibitor betrixaban, platelet inhibitors (e.g., clopidogrel), and chronic use of aspirin above low dose levels for cardio-protection per local applicable guidelines), until 4 weeks after cabozantinib has been permanently discontinued.
- Any non-protocol systemic anticancer treatment (e.g., chemotherapy, immunotherapy, radionuclides, drugs or herbal products used specifically for the treatment of the cancer under investigation).

The following therapies should be avoided until study treatment has been permanently discontinued or until otherwise specified:

- Local anticancer treatment including palliative radiation, ablation, embolization, or surgery with impact on tumor lesions should not be performed until radiographic progression per RECIST 1.1 has been established.
- Erythropoietic stimulating agents (e.g., epoetin alfa and darbepoetin alfa) should not be used based on a report of increased risk of tumor

recurrence/progression associated with erythropoietin (Wright et al 2007).

- Concomitant medications that are known to prolong the QTc interval should be avoided in subjects who receive cabozantinib until they have permanently discontinued cabozantinib treatment (refer to <http://www.qtdrugs.org> for a list of drugs which have the potential to prolong the QTc interval).
- Chronic co-administration of cabozantinib with strong inducers of the CYP3A4 family (e.g., phenytoin, carbamazepine, rifampin, rifabutin, rifapentine, phenobarbital, and St. John's Wort) may significantly decrease cabozantinib concentrations and should be avoided. Selection of alternate concomitant medications with no or minimal CYP3A4 enzyme induction potential is recommended.
- Caution must be used when discontinuing treatment with a strong CYP3A4 inhibitor in a subject who has been concurrently receiving a stable dose of cabozantinib, as this could significantly increase the exposure to cabozantinib. Co-administration of cabozantinib with strong inhibitors of the CYP3A4 family (e.g., boceprevir, conivaptan, posaconazole, ketoconazole, itraconazole, clarithromycin, atazanavir, indinavir, nefazodone, nelfinavir, saquinavir, ritonavir, lopinavir, telaprevir, telithromycin, and voriconazole) may increase cabozantinib concentrations and should be avoided. Grapefruit, star fruit, and Seville oranges may also increase plasma concentrations of cabozantinib and should be avoided.

Additional information on potential drug interactions with cabozantinib is provided in [Section 4.5.3](#).

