4.5.3 Potential Drug Interactions

Potential Drug Interactions with Cabozantinib

Cytochrome P450: Data from a clinical drug interaction study (Study XL184-008) show that clinically relevant steady-state concentrations of cabozantinib appear to have no marked effect on the area under the plasma concentration-vs-time curve (AUC) of

co-administered rosiglitazone, a CYP2C8 substrate. Therefore, cabozantinib is not anticipated to markedly inhibit CYP2C8 in the clinic, and by inference, is not anticipated to markedly inhibit other CYP450 isozymes that have lower [I]/K_i values compared to CYP2C8 (i.e., CYP2C9, CYP2C19, CYP2D6, CYP1A2, and CYP3A4). In vitro data indicate that cabozantinib is unlikely to induce cytochrome P450 enzymes, except for possible induction of CYP1A1 at high cabozantinib concentrations (30 µM).

Cabozantinib is a CYP3A4 substrate and a weak substrate for CYP2C9 (but not a CYP2D6, CYP2C8, CYP2C19, CYP2B6, or CYP1A2 substrate), based on data from in vitro studies. Results from a clinical pharmacology study, XL184-006, showed that concurrent administration of cabozantinib with the strong CYP3A4 inducer, rifampin, resulted in an approximately 77% reduction in cabozantinib exposure (AUC values) after a single dose of cabozantinib in healthy volunteers. Chronic co-administration of cabozantinib with strong inducers of the CYP3A4 family (e.g., phenytoin, carbamazepine, rifampin, rifabutin, rifapentine, phenobarbital, and St. John's Wort) may significantly decrease cabozantinib concentrations. The chronic use of strong CYP3A4 inducers should be avoided. Other drugs that induce CYP3A4 should be used with caution because these drugs have the potential to decrease exposure (AUC) to cabozantinib. Selection of alternate concomitant medications with no or minimal CYP3A4 enzyme induction potential is recommended.

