Results from a clinical pharmacology study, XL184-007, showed that concurrent administration of cabozantinib with the strong CYP3A4 inhibitor, ketoconazole, resulted in a 38% increase in the cabozantinib exposure (AUC values) after a single dose of cabozantinib in healthy volunteers. Co-administration of cabozantinib with strong inhibitors of the CYP3A4 family (e.g., boceprevir, conivaptan, posaconazole, ketoconazole, itraconazole, clarithromycin, atazanavir, indinavir, nefazodone, nelfinavir, saquinavir, ritonavir, lopinavir, telaprevir, telithromycin, and voriconazole) may increase cabozantinib concentrations. Grapefruit, star fruit and Seville oranges may also increase plasma concentrations of cabozantinib and should be avoided. Strong

CYP3A4 inhibitors should be avoided and other drugs that inhibit CYP3A4 should be used with caution because these drugs have the potential to increase exposure (AUC) to cabozantinib. Selection of alternate concomitant medications with no or minimal CYP3A4 enzyme inhibition potential is recommended.

Please refer to [Appendix C](#) for the drug interaction table lists of substrates, inducers, and inhibitors of selected CYP450 isozyme pathways.

Other Interactions: A case of a drug-drug interaction between cabozantinib and warfarin has been reported in the literature (Foxx-Lupo et al. 2016). However, a causal relationship to drug exposure for the drug-drug interaction case described above cannot be established. As a precaution, administration of warfarin at therapeutic doses is not allowed in subjects receiving cabozantinib.

In vitro data suggest that cabozantinib is unlikely to be a substrate for P-glycoprotein, but has the potential to inhibit the P-glycoprotein transport activity ($IC_{50}=7.0\ \mu M$) at high concentrations. Additional details related to these overall conclusions can be found in the investigator brochure.

Administration of the proton pump inhibitor (PPI) esomeprazole resulted in no clinically-relevant effect on cabozantinib plasma PK in healthy volunteers. Therefore, concomitant use of gastric pH modifying agents (i.e., PPIs, H_2 receptor antagonists, and antacids) is allowed in subjects administered cabozantinib.

Additional details regarding potential drug interactions with cabozantinib can be found in the investigator brochure.

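### Section 4.5.2 ties a rise in cabozantinib exposure to stopping a strong CYP3A4 inhibitor, against the protocol's own interaction data

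*Combined protocol and SAP*

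**What the plan says.** Section 4.5.2 separates therapies that are prohibited from therapies that should be avoided. Strong CYP3A4 inducers (in chronic use) and strong CYP3A4 inhibitors are in the second group.

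- **The sentence at issue** opens the inhibitor bullet: "Caution must be used when discontinuing treatment with a strong CYP3A4 inhibitor". It applies to a subject already on a stable cabozantinib dose, and its stated reason is "as this could significantly increase the exposure to cabozantinib".
- **The next sentence of that bullet** says that giving cabozantinib together with strong inhibitors "may increase cabozantinib concentrations and should be avoided".
- **Section 4.5.3** supplies the data. "Cabozantinib is a CYP3A4 substrate and a weak substrate for CYP2C9". The strong inhibitor ketoconazole "resulted in a 38% increase in the cabozantinib exposure (AUC values) after a single dose of cabozantinib in healthy volunteers". The strong inducer rifampin "resulted in an approximately 77% reduction in cabozantinib exposure (AUC values) after a single dose of cabozantinib in healthy volunteers".
- **Section 4.4.3.18**, on QT prolongation, also says that strong CYP3A4 inhibitors may raise cabozantinib plasma concentrations.
- **On inducers**, Sections 4.5.2 and 4.5.3 say to avoid chronic use of strong ones, to be careful with others because they can lower exposure, and to choose alternatives. Neither says anything about what happens when an inducer is stopped, and no other section does.

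**The concern.** If adding a drug raises exposure, taking it away should lower exposure. The sentence in Section 4.5.2 says the reverse for inhibitors. It is complete and grammatical, so a broken table or redaction does not explain it.

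The event it describes, a rise in exposure after a co-medication is withdrawn during stable cabozantinib dosing, is what the protocol's inducer data imply. The text therefore attaches the caution to the drug class for which exposure falls, and has no caution for the class for which it rises.

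This is an operative safety instruction to sites. An investigator who relies on it would look for rising exposure when an inhibitor is stopped, and would find no corresponding text when an inducer is stopped.

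**Working it through.** The plan gives no figure for stopping a co-medication, so there is none to reproduce. The check is one of direction, with a rough size.

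**Inputs (Section 4.5.3)**
- Ketoconazole added: AUC up 38%, ratio to the un-interacted level R = 1.38.
- Rifampin added: AUC down about 77%, ratio R = 1 − 0.77 = 0.23.

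**Assumptions.** Both figures are single-dose results in healthy volunteers, each for one drug. I assume that they carry over to steady state in subjects, and that the interaction reverses fully when the co-medication stops, with the cabozantinib dose unchanged.

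**Formula.** Stopping the co-medication moves exposure from R back to 1.00, so the change relative to the level just before stopping is 1/R.

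| Drug stopped | Before (un-interacted = 1.00) | After | 1/R | Change from level before | Section 4.5.2 on stopping |
|---|---|---|---|---|---|
| Strong inhibitor (ketoconazole) | 1.38 | 1.00 | 1/1.38 = 0.725 | fall of 27.5% | could rise significantly |
| Strong inducer (rifampin) | 0.23 | 1.00 | 1/0.23 = 4.35 | rise of 335% | nothing stated |

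**Range from rounding of the published percentages.** For 37.5% to 38.5%, 1/1.375 = 0.727 to 1/1.385 = 0.722. For 76.5% to 77.5%, 1/0.235 = 4.26 to 1/0.225 = 4.44.

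**Does the direction depend on the size?** No. Any R above 1 gives 1/R below 1, and any R below 1 gives 1/R above 1. The contradiction would remain if the true ratios in this population were different, provided that inhibitors raise exposure and inducers lower it, as the protocol says throughout apart from this one sentence.

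**Reference point for the 4.35.** It is relative to a level already cut to 0.23, and 0.23 × 4.35 = 1.00. Section 4.4 starts every subject at 40 mg, Table 0-1 provides only reductions, and Section 4.4.1 caps re-escalation at 40 mg/day. The protocol gives no upward adjustment for a subject on an inducer. On these figures, stopping either class returns the subject to the un-interacted exposure for the dose being taken.

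**The case against.** The case for treating this as trivial has four parts.

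1. **The reach is small.** Strong inhibitors and chronic strong inducers are to be avoided, and a drug stopped before the first dose does not meet the sentence's own condition of a stable cabozantinib dose. This largely stands, but it does not remove the case. Avoided is the weaker of the two categories in Section 4.5.2, the exclusion criteria in Section 3.2 do not name either class, and the inducer restriction covers chronic use only. Following the advice to avoid can itself mean stopping such a drug during treatment.

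2. **The right information is elsewhere.** The correct direction for inhibitors is in the same bullet, and the 77% inducer effect is in Section 4.5.3. Section 4.5.3 also refers to the investigator brochure, which is not available here. A reader might infer that sites have no protection at all. The documents do not support that: the adverse-event monitoring and dose-modification rules in Section 4.4 apply whatever the cause of a toxicity, and the sentence asks for caution, not a dose change. What remains is that one instruction conflicts with the text around it.

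3. **The size can mislead.** A reader might take 4.3-fold to mean exposure far above what the trial intends. The documents do not support that either, because the rise starts from the induced level and ends at the un-interacted one.

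4. **It is probably one error, not two.** The sentence would agree with the data if it named the other drug class, and that single change would account for both the wrong direction and the missing caution. This is plausible, but nothing in the documents confirms it, so it should not be reported as an established typing error.

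**Conclusion.** The sentence is wrong as written. Section 4.5.2 contradicts the next sentence of its own bullet, Section 4.4.3.18 and the ketoconazole result in Section 4.5.3. The rise it describes fits only withdrawal of an inducer, on which no section cautions. This is an internal contradiction in concomitant-medication safety text and not a debatable design choice.

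The direction is secure. The sizes, a fall of about 28% and a return from 0.23 to 1.00, are illustrative and rest on the carry-over and full-reversal assumptions above. How many subjects would be affected is not given and is probably few. The primary endpoint definition, sample size and error rates are unaffected. The point is worth correcting because it concerns a safety instruction and the correction is cheap.

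**What to change.** The sponsor should reconcile the sentence in Section 4.5.2 with the inducer and inhibitor text in Sections 4.5.2 and 4.5.3, so that the drug class named and the stated direction of the exposure change agree, and should tell sites of the correction. Any clinical action on starting or stopping these drugs is for the sponsor to set, and none is proposed here. The cost is about one sentence in an amendment and a site notice, with no change to the design, data collection or analysis.
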